## Table 1 – Planned study visits and collecting parameters at each visit

Procedure	Inclusion Visit 0	Visit 1 at W2	Visit 2 at W4	Visit 3 at W8
Written informed consent	X			
Assessment in accordance to inclusion/ non- inclusion criteria	X			
Assessment in accordance to exclusion criteria		X	X	X
Demographics	X			
HAMD-17	X	X	X	X
CGI -I		X	X	X
SF-36	X	X	X	X
Current treatment with other concomitant medications	X	X	X	X
Adverse events/drug reactions/ special situations reporting		X	X	X

#### Data evaluation/collection at the incusion visit (V0):

HCPs participating in the study will prospectively evaluate patient's eligibility to be enrolled in the study. Following data will be prospectively collected at the inclusion visit:

- Obtained patient's consent.
- Meeting to inclusion/non-inclusion criteria.
- Demographics.
- Confirmation of COVID 19 infection within 3 month period.
- HAMD-17 score.
- Concomitant current use of other medications.
- Quality of life assessment (SF-36).

# Data collection at the Follow up Visit (V1 – week 2):

• HAMD-17 score.

- CGI-Improvement score.
- Presence of exclusion criteria.
- Concomitant current use of other medications.
- Quality of life assessment (SF-36).
- Adverse events/drug reactions/special situations.
- Change in therapy with agomelatine if occurred or required.

#### Data collection at the Follow up Visit (V2 - week 4):

- HAMD-17 score.
- CGI-Improvement score.
- Presence of exclusion criteria.
- Concomitant current use of other medications.
- Quality of life assessment (SF-36).
- Adverse events/drug reactions/special situations.
- Change in therapy with agomelatine if occurred or required.

#### Data collection at the Final Visit (V3 - week 8):

- HAMD-17 score.
- CGI-Improvement score.
- Presence of exclusion criteria.
- Concomitant current use of other medications.
- Quality of life assessment (SF-36).
- Adverse events/drug reactions/special situations.
- Change in therapy with agomelatine if occurred or required.

## The scheme of TELESPHOR study

#### Statistical analysis

Due to non-interventional nature of the study design descriptive statistical methods will be used. Search statistical analysis will be performed in the following groups of patients: in the clinical study the primary end point of the study is a mean change from BL in HAMD-17 total score assessed at week 8 of the observational period.

In the article of O.V. Vorob'eva "Valdoxan in the Treatment of Depression in Neurological Practice: Results of the Russian Multicenter Naturalistic Study "Resonance" from Zhurnal Nevrologii i Psikhiatrii imeni S. S. Korsakova, Vol. 112, No. 9, Iss. I, pp. 47—51, September, 2012, was described the efficacy and tolerance of Valdoxan (agomelatine) in mild and moderate depression due to neurological diseases. Treatment efficacy was evaluated using standard psychometric tools, one of them was the 17-point Hamilton depression scale (HAMD-17).

The mean total score on the HAMD-17 was  $15.3 \pm 3.8$  points. Significant decreases in total points scores on the HAMD-17 were seen by the end of the first week of treatment. After completion of treatment courses (at six weeks of treatment), the mean score was  $4.7 \pm 3.2$  points. At six weeks of treatment, responders (patients with total HAMD-17 scores which decreased at least twofold) constituted 82.33% of all patients treated.

The following general assumptions were made for the sample size calculations:

1) One-sided (directional) statistical hypothesis for mean:

H0:  $m1 - m0 \le 0$ HA:  $m1 - m0 \ge 0$ 

where m1 stands for sample (study) mean of the corresponding variable (change from BL in HADS total score assessed at week 8 of the observational period), and m0 stands for the population mean (constant).

2) Possible standard deviation is 3.8 points

- 3) Planned study power is 90%, accordingly, type II ( $\beta$ ) error is 0.1
- Overall significance level is 0.01 that corresponds to two-sided type I (α) error of 0.01 or one-sided type I (α) error of 0.005
- 5) Dropout during the study period to 30%.

Calculations for each of the parameters listed above were performed using the validated PASS sample size calculation software, with main outputs (screenshots) provided under the assumptions summarized above.

Numeric Results Hypotheses: H0: μ ≤ μ0 vs. H1: μ > μ0									
_		_		Diff		Effect		_	
Power	N	μ0	μ1	μ1 - μ0	σ	Size	Alpha	Beta	
		0	0,0	0,0	3,8	0,00000	0,005		
0,90031	861	0	0,5	0,5	3,8	0,13158	0,005	0,09969	
0,90127	219	0	1,0	1,0	3,8	0,26316	0,005	0,09873	
0,90059	99	0	1,5	1,5	3,8	0,39474	0,005	0,09941	
0,90571	58	0	2,0	2,0	3,8	0,52632	0,005	0,09429	
0,90242	38	0	2,5	2,5	3,8	0,65789	0,005	0,09758	
0,90991	28	0	3,0	3,0	3,8	0,78947	0,005	0,09009	
0,90091	21	0	3,5	3,5	3,8	0,92105	0,005	0,09909	
0,90346	17	0	4,0	4,0	3,8	1,05263	0,005	0,09654	

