## Study variables

## **Primary variables:**

• Mean change from baseline (BL) in total HAMD-17 score assessed at week 8 of the observational period.

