# Selection of the study population

# **Inclusion criteria**

- 1. Obtained signed informed consent from the patient.
- 2. Age of 18-65 years old.

- 3. Out-patient with confirmed COVID 19 infection within 3 months period before the date of inclusion.
- 4. Confirmed depression with total HAMD-17 score of 8-24 required treatment with antidepressive medicines.
- 5. Decision to administer agomelatine preceeds the decision to include a patient in the study.

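### Do the wrong scale name, the undefined sign and the unsourced SD of 3.8 in the sample-size assumptions undermine the planned study size?

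*Combined protocol and SAP*

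**What the plan says.** The section on primary variables gives the endpoint as "Mean change from baseline (BL) in total HAMD-17 score assessed at week 8 of the observational period". The opening of the Statistical analysis section repeats HAMD-17 as the primary endpoint. Assumption 1 of the sample-size calculation then describes the study mean as that of the "change from BL in HADS total score assessed at week 8 of the observational period". It sets a one-sided hypothesis in which both H0 and HA, as typed, include zero. The PASS output heads its table "H0: μ ≤ μ0 vs. H1: μ > μ0", with μ0 = 0 and every non-trivial μ1 positive.

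Assumption 2 reads "Possible standard deviation is 3.8 points", with no source. The cited naturalistic study, in "mild and moderate depression due to neurological diseases", reports HAMD-17 of 15.3 ± 3.8 at the start and 4.7 ± 3.2 at six weeks. Its responders "constituted 82.33% of all patients treated".

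The conclusion under One-Sample T-Tests is that 28 patients give 90% power for 3.0 points at one-sided 0.005, which becomes 40 after 30% dropout, and that at least 100 will nevertheless be invited. Study design and methodology expects 20 physicians to enrol at least 5 patients each. The Statistical analysis and Biometrics sections both call the analysis descriptive.

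**The concern.** Three features make the calculation hard to trace to the primary variable.

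- **Scale.** HADS is a different instrument from HAMD-17. It is absent from Table 1 and from the data lists for all four visits. Taken literally, the hypothesis cannot be tested with the study's data.
- **Sign.** Improvement on HAMD-17 is a fall. If change means week 8 minus baseline, a 3-point improvement is −3, and an upper-tail test has essentially no power to detect it.
- **SD.** A one-sample test of change needs the SD of the within-patient change. The value 3.8 equals the spread of the cited study's starting score, which is a different quantity. If the true SD of change were larger, 28 evaluable patients would give less than 90% power.

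At stake is whether the stated 28 evaluable and 40 enrolled hold for the HAMD-17 change, and whether the study could be too small.

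**Working it through.** **Inputs from the Statistical analysis section:** SD 3.8; one-sided α 0.005; power 90%; difference 3.0; dropout 30%; cited SDs 3.8 (start) and 3.2 (six weeks). The baseline-to-endpoint correlation r is not in the documents and is assumed.

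**Step 1: the plan's own figure.** Power of the one-sample t-test is P(T > t₀.₉₉₅,ₙ₋₁), where T is noncentral t with n − 1 degrees of freedom and noncentrality (δ/σ)√n. With δ = 3.0, σ = 3.8 and n = 28, power is 0.90991, as printed. 28/0.7 = 40. All rows from 1.0 to 4.0 points match exactly. The 0.5-point row gives 863 against the printed 861, which is immaterial.

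**Step 2: scale.** Replacing HADS by HAMD-17 changes no number, because every input is already a HAMD-17 figure.

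**Step 3: sign.** With change as week 8 minus baseline, the upper-tail test has power of about 3 × 10⁻¹¹ at n = 28 for a 3-point improvement. With baseline minus week 8 it has the printed 0.90991. Only the second reading fits the table. The PASS heading also gives the strict alternative that the typed HA lacks.

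**Step 4: SD of change.** SD = √(3.8² + 3.2² − 2r × 3.8 × 3.2) = √(24.68 − 24.32r).

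| Assumed r | SD of change | Power, n = 28 | Evaluable / enrolled for 90% | Power, n = 70 | Detectable at 90%, n = 70 |
|---|---|---|---|---|---|
| 0 | 4.97 | 66% | 45 / 65 | 99.1% | 2.35 |
| 0.25 | 4.31 | 81% | 35 / 50 | 99.9% | 2.04 |
| 0.42 | 3.80 | 91% | 28 / 40 | >99.9% | 1.80 |
| 0.5 | 3.54 | 95% | 25 / 36 | >99.9% | 1.67 |

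An SD of 3.8 corresponds to r = 10.24/24.32 = 0.42, which lies inside this range. With 28 evaluable, 90% power for 3.0 points holds up to an SD of 3.86. With 70 evaluable (100 × 0.7) it holds up to 6.35.

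**Step 5: does the responder rate settle r?** Let X be the baseline score and Y the end score, bivariate normal. Response is Y ≤ X/2. The mean of Y − X/2 is 4.7 − 7.65 = −2.95. A rate of 82.33% gives z = 0.928, so the SD of Y − X/2 is 2.95/0.928 = 3.179. Then r = (3.2² + 3.8²/4 − 3.179²)/(3.8 × 3.2) = (13.85 − 10.105)/12.16 = 0.31, and the SD of change is 4.15. Rounding the same model to integer scores gives r of about 0.17 and SD 4.53. A right-skewed (gamma) end score gives r = 0.13 and SD 4.63. An SD of 3.8 would imply 84.1% responders, only 1.8 points from the cited rate. The cited study's size is not given. At an assumed 400 patients the 95% interval is 82.33% ± 1.96√(0.8233 × 0.1767/400), or 78.6% to 86.1%. Under the normal model, r = 0 gives 78.6% and r = 0.5 gives 85.5%, so the interval spans that whole range. The rate does not identify r.

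**The case for a change.** The strongest case for acting is that a plan stating a hypothesis, an α and a power should state them for its own primary variable. Surplus patients do not correct a hypothesis that names the wrong scale. The 28-patient figure also has little margin: 90% power is lost once the SD of change passes 3.86, and each of the three responder-rate models gives a larger SD (4.15 to 4.63). The edits would be wording only.

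Much of this stands as description. HADS is wrong, the sign is unstated, and 3.8 has no stated source as an SD of change. What does not stand is the step to a different SD or sample size. Those three models disagree among themselves and leave out sampling error and how unassessed patients were counted, so writing any one of their SDs into the plan would replace one unsupported value with another. The 90% claim is conditional on an SD the plan openly calls possible, and under that SD it is exact. The cited fall is 15.3 − 4.7 = 10.6 points. Even at an SD of 4.97, 28 patients give essentially 100% power for a fall of that size.

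**Conclusion.** No change follows. The scale name is a clerical slip that the opening of the same section and the primary-variable definition correct. The sign is fixed by the PASS table. The SD is an untraced planning assumption that falls within the range the cited figures allow.

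If the SD of change lies between 3.54 and 4.97, the 3.0-point scenario needs 25 to 45 evaluable patients (36 to 65 enrolled). The planned 100 exceed all of these. About 70 evaluable give at least 99% power for 3.0 points, and 90% power for a difference of 1.7 to 2.35 points. The primary result is a descriptive mean change, so neither its calculation nor its reading depends on these inputs.

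This rests on four assumptions: the ± values are SDs; the six-week spread applies at week 8; the cited neurological population carries over to post-COVID patients with HAMD-17 of 8 to 24; and r is not negative. It also assumes that 100 are enrolled. One section says invited, but the site estimate of 20 × 5 = 100 supports enrolment. The margin is wide: at 70 evaluable, 90% power for 3.0 points is lost only if the SD of change exceeds 6.35.

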#### **One-Sample T-Tests**

#### References

Zar, Jerrold H. 1984. Biostatistical Analysis (Second Edition). Prentice-Hall. Englewood Cliffs, New Jersey.

As can be seen from the various scenarios provided depending on the planned difference, approximately 28 study subjects will be enough to detect at least a 3.0-point difference between the sample and population means with 90% power at 0.005 one-sided significance level. Dropout-Inflated Enrollment Sample Size is 40 study subjects.

Despite that sample size calculation is 40 patients, at least 100 patients with MDD will be invited to participate in the study.

#### **Safety**

Definitions

Pharmacovigilance information

Pharmacovigilance data include any unintended or adverse event associated with the use of a medicinal product in humans, whether or not considered drug related, including the following special situations (situations where no adverse event occurred but information needs to be collected):

- exposure during pregnancy or breastfeeding;
- overdose, abuse, misuse, off-label uses, medication error, occupational exposure (including professional one);
- lack of efficacy.
- any suspected transmission via a medicinal product of an infectious agent,
- unintended therapeutic benefit.

## Adverse event (AE)

Adverse event (AE) is any untoward medical occurrence in a patient or clinical-trial participant administered the medicinal product, which does not necessarily have a causal relationship with the use of this medicinal product.

An adverse event can therefore be any unfavorable and unintended sign (e.g. an abnormal laboratory finding), symptom, or disease temporally associated with the use of a medicinal product, whether or not considered as related to the medicinal product.

## Adverse (drug) reaction (ADR)

- Adverse reaction (synonyms: Adverse drug reaction, Suspected adverse (drug) reaction, Adverse effect, Undesirable effect) is a response to a medicinal product which is noxious and unintended.
- Response" in this context means that a causal relationship between a medicinal product and an adverse event is at least a reasonable possibility.
- Adverse reactions may arise from use of the product within or outside the terms of the marketing authorization or from occupational exposure. Conditions of use outside the marketing authorization include off-label use, overdose, misuse, abuse and medication errors.

#### Serious adverse (drug) reaction (SADR)

Serious adverse reaction is an adverse reaction, which results in death, is life-threatening, requires in-patient hospitalisation or prolongation of existing hospitalisation, results in persistent or significant disability or incapacity, or is a congenital anomaly/birth defect.

Life threatening in this context refers to a reaction in which the patient was at risk of death at the time of the reaction; it does not refer to a reaction that hypothetically might have caused death in case of more severe course.

Medical and scientific judgement should be exercised in deciding whether other situations should be considered as serious reactions, such as important medical events that might not be immediately life threatening or result in death or hospitalisation but might jeopardize the patient or might require intervention to prevent one of the other outcomes listed above.

Examples of such events are intensive treatment in an emergency room or at home for allergic bronchospasm, blood dyscrasias or convulsions that do not result in hospitalisation or development of dependency or abuse.

Any suspected transmission via a medicinal product of an infectious agent is also considered as a serious adverse reaction.

#### Responsibilities

- Events to be reported
- All available information about the following events reported during the study will be recorded:

All serious adverse drug reactions related to the use of Agomelatine

- All non-serious adverse drug reactions related to the use of Agomelatine
- All reports about special situations (see section Pharmacovigilance information)

#### • All adverse events

Specific attention should be paid to increase of ALT and/or AST, ALP value >3 ULN and increase of total bilirubin > 2 ULN.

#### **Responsibilities of investigator**

In prospective studies, at medical visits the investigator will ask a participating patient to indicate whether or not an adverse event (serious or not) has occurred.

Investigator has to assess causal relationship between an adverse event and the investigated drug intake, as well as the seriousness criteria and later on the outcome of the event.

In case of Adverse Events, Adverse Drug Reactions or special situations that occurs during the study (both serious and non-serious), the investigator must complete the "Adverse event / Adverse drug reaction / Special Situation Reporting Form" (Appendix 4) without waiting for the clinical outcome or the results of additional investigations.

If the event is serious, it will be notified immediately (same or next working day at the latest) to Servier company in Russia via e-mail to address [contact] or by fax to number [name]. The anonymized copies of all the available and relevant laboratory findings, hospitalisation reports or other investigation results performed in connection with the adverse event should be attached to the form.

All other events should be reported by investigator within 2 working days.

The same rules apply for the transferring of additional information about the event.

The investigator must ensure the appropriate follow-up of the patient depending on the nature of event, until it resolves. The investigator will continue to notify follow up data according to timeframes defined above.

If investigator does not follow-up a patients anymore (i.e. in case of hospitalization followed by the treatment by specialist or the participant's general practitioner,...), he/she will do every effort to contact the specialist or department in charge of follow-up of the patient, so as to have additional information and report it to Servier company in Russia.

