## Secondary objectives

- To describe effectiveness of agomelatine on anxiety symptoms associated with the depression and assessed by HAMD-17 (point 10 and 11) after 8 weeks of treatment of patients included in the study.
- To describe effectiveness of agomelatine on global improvement and social functioning assessed by CGI score after 8 weeks of treatment of patients included in the study.
- To describe effectiveness of agomelatine on quality of life in patients with depression episode occurred after COVID-19 assessed by SF-36 questionnaire after 8 weeks of treatment of patients included in the study.
- To describe tolerability of agomelatine after 8 weeks of treatment based on rate of adverse events leading to drug discontinuation in patients included in the study.

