#### Secondary variables:

- % of patients defined as responders to the treatment (HAMD-17 total score decrease ≥ 50%) at week 8 of the observational period.
- % of patients achieving disease remission (defined as HAMD-17 total score < 7) at week 8 of the observational period.
- Mean change from BL in HAMD-17 point 10 "psychological anxiety" assessed at week 8 of the observational period.
- Mean change from BL in HAMD-17 point 11 "somatic anxiety" assessed at week 8 of the observational period.
- Mean change in scores of the Clinical Global Impression scale (CGI), item 2 (global improvement) at W2,W4,W8 assessed at week 8 of the observational period.
- Mean change from BL in total score of the SF-36 QoL questionnaire reported by patients at week 8 of the observational period.
- Mean change from BL in score of the SF-36 QoL questionnaire (physical component) reported by patients at week 8 of the observational period.
- Mean change from BL in score of the SF-36 QoL questionnaire (psychiatric component) reported by patients at week 8 of the observational period.

• Number of adverse events/ adverse drug reactions leading to drug discontinuation during the observational period.

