# Study plan and procedures

A patient with depression occurred within 3 month period after onset of confirmed COVID 19 infection who has already been recommended to initiate antidepressive treatment with agomelatine will be asked to provide a consent to participate in the study and in case of consent is positive the patient will be invited for 3 more visits starting from the date of the inclusion in the study according to clinical practice. Therefore clinical parameters needed for describing effectiveness and tolerability of agomelatine treatment will be prospectively collected at each of these visits.

Antidepressive treatment of enrolled outpatients can be modified by investigating psychiatrist or neurologist at any time of the observation if required.

Following visits are planned:

- 1. Inclusion Visit 0 (V0) inclusion in the study
- 2. Follow up Visits 1-2 (V1-V2) visits at week 2 and week 4 after V0.
- 3. Final Visit 3 (V3) visit at week 8 after V0.

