#### Confidentiality of patient data

• Researchers are required to maintain the confidentiality of information about patients included in this study. Confidential data should contain enough information to contact the patient in case of an emergency, or if further monitoring is required.

To protect data privacy and keep patients anonymous, their identity will be encoded in the research documentation. Patients can be identified using a unique number that will be recorded and the CRF. In order to reveal the patient's identity, all researchers will have a confidential list of patient identification containing the names and phone numbers. Thus, only the researcher will be able to decode the patient's identity.

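### No step is specified to find out about adverse events or the reason for stopping in patients who do not return, so the rate of adverse-event discontinuation may be underestimated.

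*Combined protocol and SAP*

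**What the plan says.** All references are to the combined protocol and SAP.

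- **Enquiry.** Under Responsibilities of investigator, "at medical visits the investigator will ask a participating patient to indicate whether or not an adverse event (serious or not) has occurred".
- **Schedule.** Under Study plan and procedures, "the patient will be invited for 3 more visits starting from the date of the inclusion in the study according to clinical practice". In Table 1 the row "Adverse events/drug reactions/ special situations reporting" is marked at weeks 2, 4 and 8. There is no early-termination visit and no row for contact after a missed visit.
- **Drug stops.** The lists for V1, V2 and V3 each carry the item "Change in therapy with agomelatine if occurred or required". None asks for the reason for stopping.
- **Tolerability.** The secondary objective is "based on rate of adverse events leading to drug discontinuation in patients included in the study". The matching secondary variable is a number of adverse events or reactions "leading to drug discontinuation during the observational period". No other tolerability variable is defined.
- **Dropout.** Assumption 5 of the sample size calculation reads "Dropout during the study period to 30" per cent.
- **Denominator.** The Biometrics section computes relative frequencies only over patients with data on the variable concerned.
- **Contact data.** Under Confidentiality of patient data, "Confidential data should contain enough information to contact the patient in case of an emergency, or if further monitoring is required". Investigators hold a list of names and phone numbers. No procedure uses it after a missed visit.

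**The concern.** The event to be counted can be the reason a patient leaves. A patient who stops agomelatine because of a side effect and then stays away meets no scheduled question about either the event or the stop. If such patients are kept in the denominator, each counts as having had no event. If they are dropped from it, the rate describes only those who kept attending. Neither choice supplies the missing numerator.

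At stake is the one tolerability result the study will report. The same gap can leave serious events in non-returners unreported, and it can leave the reason for some missing week-8 HAMD-17 scores unknown, which makes the primary variable harder to interpret.

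**Working it through.** **1. The plan's own dropout figure.** A one-sample, one-sided t-test with n = 28, difference 3.0, SD 3.8 and alpha 0.005 has power 0.90991 by the noncentral t distribution, as printed in the plan. Inflating for dropout gives 28 / (1 − 0.30) = 40, also as printed. So 30% is an all-cause allowance for enrolment. The plan states no sample size or precision for tolerability.

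**2. How many patients could be affected.** The plan intends at least 100 patients. At the ceiling, 100 × 0.30 = 30 leave early. That is an upper bound on those not asked after their last attended visit, because some leave with the reason recorded.

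**3. Which patients the written duties reach.**

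| Patient's course | Reached? |
|---|---|
| Stops the drug, attends the next visit | Yes: visit enquiry and therapy-change item |
| Reports the event to the site without being asked | Yes: a form is required for any event during the study |
| Meets an exclusion criterion at a visit | Yes: checked at V1 to V3 |
| Has a known event and is then treated elsewhere | Yes: the investigator must try to contact the treating specialist or department |
| Stops the drug, says nothing, does not return | No specified step |

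**4. Size of a possible undercount.** Let s be the share of the 30 who stopped because of an adverse event that never reached the site. Missed stops = 30 × s. The documents do not give s, so the full range is shown. Assume also that 5 such stops were recorded, all in patients who kept attending. True rate = (5 + 30s) / 100.

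| s | Missed | True rate | Reported, 5/100 | Reported, 5/70 |
|---|---|---|---|---|
| 0% | 0 | 5% | 5.0% | 7.1% |
| 10% | 3 | 8% | 5.0% | 7.1% |
| 25% | 7.5 | 12.5% | 5.0% | 7.1% |
| 50% | 15 | 20% | 5.0% | 7.1% |
| 100% | 30 | 35% | 5.0% | 7.1% |

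If the 5 recorded stops were instead among the 30 who left, at most 30 − 5 = 25 could be missed, and the top of the range would be (5 + 25) / 100 = 30%.

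**5. Effect of the denominator.** Over all 100, any missed stop lowers the reported rate. Over the 70 with data, the rate is too low only if (5 + 30s) / 100 > 5/70, that is 30s > 2.14, or s > 7.1%. In words, the lost patients must have a higher rate than those who stayed. Below that value the available-case rate is too high. The direction of error is therefore likely rather than certain.

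**The case against.** The strongest reply is that the plan does not confine safety information to visits. A form is required for any event that occurs during the study, however the site hears of it. Known events are followed until they resolve, and the investigator must make every effort to reach whoever now treats the patient. Treatment may be modified at any time, so contact outside V1 to V3 is possible. All adverse events are coded and listed, not only those that led to stopping. The study is descriptive, tolerability is a secondary objective, and most of the documentation forms are not among the documents, so a reason-for-withdrawal item cannot be excluded.

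Much of this stands, and it rules out several stronger readings:

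- A reader might infer that nobody contacts patients who do not return. The plan is silent on this; it neither forbids nor excludes contact.
- A reader might take the 30% as a forecast of silent losses. It is an all-cause allowance, and it includes documented exits such as a transaminase rise found at a visit. For the same reason it does not follow that every missing week-8 score lacks a reason.
- A reader might infer that a confidence interval would fail to cover the true rate. With an assumed 3 recorded stops, the exact 95% upper limit is 8.5% for 3/100, below a true rate of (3 + 6)/100 = 9%. For 3/70 the limit is 12.0%, which covers 9%. No general statement about coverage holds.
- That side effects are a usual reason for not returning is plausible, but the documents give no reasons for dropout.

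What the reply does not meet is the last row of the table in step 3. Each duty cited starts from an event or a transfer of care that the site already knows of. Listing all events cannot recover one that nobody asked about, and a withdrawal item on a form needs a contact before it can be filled in.

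**Conclusion.** The point holds as an omission with a plausible direction. Scheduled enquiry is tied to attended visits, nothing specified reaches a patient who simply stops coming, and the only tolerability variable can miss events in patients who left because of one. The rate may be underestimated.

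At 100 included and the 30% ceiling, the number affected lies between 0 and 30. The rates in step 4 rest on an assumed 5 recorded stops and an assumed share; they show what is possible, not what is expected. The documents do not support saying that the rate is biased by a known amount. The gap is still worth closing before enrolment, because it cannot be repaired afterwards.

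**What to change.** Add to Responsibilities of investigator and to the V1 to V3 data lists:

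1. For each patient who stops attending, the investigator makes one contact attempt using the existing confidential list. The trigger is the end of attendance, not every missed visit, and the protocol should define it and set a time limit.
2. The contact records whether and when agomelatine was stopped, the reason (adverse event, lack of efficacy, other, unknown) and any adverse event.
3. Events found this way count in the tolerability variable, with all included patients as the denominator.
4. The report states how many patients could not be reached, and gives the rate with them counted as no event and as event.

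Cost: a short amendment with ethics review, one form line and, at the planned ceiling with 100 included, about 30 calls at most. Over 20 physicians that is 30 / 20 = 1.5 calls each, with no extra staff. A call for every missed visit would cost more: a patient lost before V1 misses three visits, so 30 losses could mean up to 30 × 3 = 90 calls.
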